11.3. Appendix 3: Country Specific Requirements

11.4. Appendix 4: Liver Chemistry Stopping and Followup Criteria

## **Description:**

- The purpose of this RAP is to describe the planned analyses and output to be included in the Clinical Study Report for Protocol HZC102972 (2012N150072\_01).
- This RAP is intended to describe the final analyses required for the study.
- This RAP will be provided to the study team members to convey the content of the Statistical Analysis Complete (SAC) deliverable.

# 1. INTRODUCTION

The purpose of this reporting and analysis plan (RAP) is to describe the analyses to be included in the Clinical Study Report for Protocol HZC102972:

Revision Chronology:			
2012N150072_00	07-JAN-2013	Original	
2012N150072_01	14-AUG-2013	Amendment No.: 01 This protocol amendment is being implemented to revise and clarify exclusion criteria concerning participation in pulmonary rehabilitation programs; clarify the description of DEXA procedures and clinical labs; correction of typographical errors.	

# 2. SUMMARY OF KEY PROTOCOL INFORMATION

# 2.1. Changes to the Protocol Defined Statistical Analysis Plan

Changes from the originally planned statistical analysis specified in the protocol are outlined in Table 1.

[figure not shown]
Table 1 Changes to Protocol Defined Analysis Plan

Protocol	Reporting & Analysis Plan	
Statistical Analysis Plan	Statistical Analysis Plan	Rationale for Changes
The percent change from baseline in BMD for the total hip will be the primary endpoint, and analysed using a repeated measures model with terms for treatment, time, time by treatment, baseline BMD, baseline BMI and gender.	The primary endpoint will be analysed using a repeated measures model with terms for treatment, visit, visit by treatment, baseline BMD, baseline BMI, age and gender. Weighted contrasts will be formed between all visits to calculate the average change per year over the 3 year study treatment period.	The wording in protocol used time and not visit, which may imply time as a continuous variable, rather than categorical. The analysis was clarified in the RAP text. Additional text added around contrast statement as use of SAS code in RAPs is now discouraged. In addition, age was missed from the model
Only included analysis of the ITT population	Safety and ITT population will be defined.	As this is a safety and not an efficacy study it is more appropriate to use the Safety population.
Section 8.2.2 of the Protocol Sample Size Sensitivity – the power calculations are inconsistent	Section 2.5 of this RAP provides the amended power calculations	Previous power calculations for sample size sensitivity were inconsistent, and have been corrected.

# 2.2. Study Objective(s) and Endpoint(s)

Objectives	Endpoints
Primary Objectives	Primary Endpoints
Evaluate the effect of FF/VI on BMD at the total hip	BMD measured at the total hip
Secondary Objectives	Secondary Endpoints
Evaluate the effect of FF/VI on BMD by gender	BMD measurements by gender
Evaluate the effect of FF/VI on BMD as assessed at the lumbar spine L1-L4	BMD measured at the lumbar spine (L1-L4)
Other Objectives	Other Endpoints
Evaluate safety of FF/VI	Adverse Event reporting
	Serious Adverse Event reporting
	Incidence of Fractures
	Incidence of Pneumonias
	COPD exacerbations

## 2.3. Study Design

# 2.4. Statistical Hypotheses / Statistical Analyses

The null hypothesis for the primary measure is that the decrease in BMD assessed at the total hip is larger for the FF/VI combination product arm compared with the VI arm. The alternative hypothesis that the change in BMD assessed at the total hip is not worse for the FF/VI arm compared with the VI arm. The 95% confidence interval will be compared to a lower bound of -1%/year in order to assess clinical non-inferiority such that:

$$H_0$$
:  $\mu_{FF/VI} \le \mu_{VI} - 1\%$   
 $H_1$ :  $\mu_{FF/VI} \ge \mu_{VI} - 1\%$ 

This is also the null and alternative hypothesis for the secondary measure of BMD assessed at the L1-L4 lumbar spine.

## 2.5. Sample Size Sensitivity

For the primary endpoint of BMD at the total hip, males and females will be combined in order to have >90% power to demonstrate non-inferiority. This will be done by comparing the lower boundary of a two-sided 95% confidence interval of the treatment difference to -1 % year, assuming a true treatment difference of -0.3 %/year with a standard deviation of 1.3 %/year.

As detailed in Section 2.1, the power calculations for sample size sensitivity given in the protocol were inconsistent, and hence have been corrected as shown in Table 2. These demonstrate that across a true treatment difference of -0.2 to -0.4 %/year and a true standard deviation of 1.3 to 1.5 %/year, the primary endpoint of BMD at the total hip for males and females combined will have at least 85% power.

Table 2 Sample Size Sensitivity

	True Treatment Difference between FF/VI and VI			
SD	-0.2%/yr	-0.3%/yr	-0.4%/yr	
1.3%/yr	>99%	98%	93%	
1.4%/yr	99%	96%	89%	
1.5%/yr	98%	94%	85%	

# 3. PLANNED ANALYSES

## 3.1. Final Analyses

The final planned primary analyses will be performed after the completion of the following sequential steps:

- 1. All subjects have completed the study as defined in the protocol.
- 2. All required database cleaning activities have been completed and final database has been released (DBR).
- 3. All criteria for unblinding the randomisation codes have been met.
- 4. Randomisation codes have been unblinded and distributed according to the unblinding procedures.
- 5. Database freeze (DBF) has been declared by Data Management.

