#### 4.1. Protocol Deviations

Important protocol deviations (including deviations related to study inclusion/exclusion criteria, conduct of the trial, patient management or patient assessment) will be summarised and listed.

Protocol deviations will be tracked by the study team throughout the conduct of the study in accordance with the Protocol Deviation Management Plan Version 2 (26-Sep-2016) or higher.

- Data will be reviewed prior to unblinding and freezing the database to ensure all important deviations are captured and categorised on the protocol deviations dataset.
- This dataset will be the basis for the summaries and listings of protocol deviations.

A separate summary and listing of all inclusion/exclusion criteria deviations will also be provided. This summary will be based on data as recorded on the inclusion/exclusion page of the eCRF.

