#### 6.3. Concomitant Medications

Medications categorised as 'Other medications' will include medications not used to treat COPD or low bone mineral density [BMD] and will be summarised by Anatomical-Therapeutic-Chemical (ATC) level 1 and ingredient. COPD medications not given for an exacerbation will be summarised by Respiratory Medication Class (RMC). COPD medications given for exacerbations whilst on treatment will also be summarised by RMC. Multi-ingredient medications will be presented according to their combination ATC classification rather than the classifications of the individual ingredients.

BMD medications, taken to improve bone mineral density, will be summarised by treatment group and overall. Bone mineral density medications will be identified using ATC codes along with reviewing all concomitant medications prior to database freeze to ensure all relevant medications are included.

COPD, BMD and Other medications will be listed separately. The COPD medications listing will indicate whether each medication was taken for an exacerbation. Listings will indicate in which study phases each medication was taken (pre-treatment and/or on-treatment and/or post-treatment).

A listing of the relationship between ATC Level 1, ingredient and verbatim text will be produced for 'Other medications' only.

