## 7.4. Adverse Events of Special Interest Analyses

A comprehensive list of MedDRA terms based on clinical review will be used to identify each type of event. Changes to the MedDRA dictionary may occur between the start of the study and the time of reporting and/or emerging data from on-going studies may highlight additional adverse events of special interest, therefore the list of terms to be used for each event of interest and the specific events of interest will be based on the safety review team (SRT) agreements in place at the time of reporting. These will be produced for both LABA and ICS AESIs. The details of the planned displays are provided in Appendix 12: List of Data Displays.

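### The BMD-medication review and the special-interest event list have deadlines that fall after unblinding, so both can be settled with treatment known

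*SAP*

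**What the plan says.** SAP 3.1 states that the final analyses "will be performed after the completion of the following sequential steps". In short, the five steps are: all subjects complete; cleaning done and database released; unblinding criteria met; "Randomisation codes have been unblinded and distributed according to the unblinding procedures"; and "Database freeze (DBF) has been declared by Data Management".

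Three places in the SAP set deadlines for classification decisions:

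- **Section 6.3, BMD medications.** These are identified from ATC codes "along with reviewing all concomitant medications prior to database freeze to ensure all relevant medications are included".
- **Section 7.4, adverse events of special interest.** The term lists and the choice of events "will be based on the safety review team (SRT) agreements in place at the time of reporting". Section 9.6.3 adds that the list is to be updated and re-reviewed if its reference data change between approval of the plan and reporting. The list includes a category for reduced bone density and related fractures.
- **Section 4.1, protocol deviations.** "Data will be reviewed prior to unblinding and freezing the database".

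**The concern.** Section 4.1 names two milestones, unblinding and freeze. Section 6.3 names only freeze, which section 3.1 places after unblinding. Sections 7.4 and 9.6.3 name only reporting, which is later still. Nothing in these three sections requires the decision to be made blind.

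Both decisions involve judgement. Someone must decide whether a drug was taken to improve bone density, and which preferred terms belong in a bone-related category. In a double-blind trial whose purpose is bone safety, such decisions should be demonstrably made without knowledge of treatment.

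What is at stake is interpretation. SAP 7.1.4 defines the estimand as FF/VI with or without BMD medication or systemic corticosteroids, against VI on the same terms, and keeps BMD data recorded after such medication. If bone drugs were started more often on FF/VI, they could mask bone loss and favour non-inferiority. The BMD-medication displays are where a reader would look for that imbalance, so the classification behind them needs to be above suspicion. The special-interest tables are a second place where a reader will look for bone harm.

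**Working it through.** No arithmetic applies: the point concerns the order of steps and depends on no effect size, SD, margin or sample size. The check sets each deadline against the sequence in SAP 3.1.

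**Deadlines**

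| Decision | Source | Deadline | Must it precede unblinding (step 4)? |
|---|---|---|---|
| Data cleaning and release | SAP 3.1 | Step 2 | Yes, by order |
| Protocol deviations | SAP 4.1 | Before unblinding and before freeze | Yes, explicitly |
| BMD-medication review | SAP 6.3 | Before freeze (step 5) | No |
| Special-interest events and terms | SAP 7.4, 9.6.3 | Reporting | No |

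A review done between steps 4 and 5 satisfies section 6.3 but is unblinded. Reporting follows all five steps, so a list that may change until reporting may change after unblinding.

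**What each decision feeds**

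1. *Primary and secondary BMD analyses.* SAP 7.1.4 retains BMD data after BMD medication. The model in 7.1.5.1 has terms for treatment, visit, their interaction, log baseline BMD and its interaction with visit, BMI, age and gender. BMD medication is not a term. Nor is it among the covariates in 5.4.1 or the potential subgroups in Table 3. Section 7.2 uses the same event strategy and refers back to the same model. Calling a drug a BMD medication or an other medication therefore changes no data point, estimate or confidence interval.
2. *Fractures.* Protocol 6.2.5 records them on a dedicated eCRF page. SAP 7.5 and Table 2.23 summarise them without using the special-interest terms.
3. *Medication displays.* Moving a drug between the two classes moves it between Tables 1.24 and 1.25 (BMD) and Tables 1.26 and 1.27 (other), and between Listings 37 and 38.
4. *Special-interest outputs.* Changing the list changes Tables 2.47 and 2.48 and Listing 31.

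Items 1 and 2 are unaffected. Items 3 and 4 are exposed.

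**The case against.** Several points on the other side carry weight.

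- **Triggers for changing the special-interest list are external.** Sections 7.4 and 9.6.3 cite MedDRA changes, emerging data from other studies and updates to a reference dataset, not this trial's results. The categories are already listed, many rest on standardised queries, and a listing of all preferred terms used is planned. This stands and narrows the discretion. It does not remove it: the bone category combines an osteoporosis/osteopenia query with individually chosen terms that the SAP does not enumerate, and safety review team agreements run to reporting.
- **All adverse events are tabulated anyway.** Table 2.30 shows every on-treatment event by preferred term. This stands: a change to the list could regroup events but not hide them.
- **The plan is completed before unblinding.** Protocol 8.3.3.1 commits to this, and the ATC method and the category list are in the plan. But a plan finished blind can still contain deadlines that fall after unblinding, and these do.
- **Unseen procedures may close the gap.** The unblinding criteria and procedures in steps 3 and 4 are not reproduced and could require a blinded review. No section says so for these two items.

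A reader might infer more than the documents support:

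- *That the primary result is at risk*, because BMD-medication use is a named intercurrent event. It is not, since the data are kept and the medication is not modelled.
- *That fracture counts depend on the special-interest list.* They have their own collection and summary.
- *That recorded data may be altered after unblinding.* Cleaning and release come at step 2, and no section provides for data changes between steps 4 and 5.
- *That the order in 3.1 must be reversed.* Release and freeze are not defined in the SAP, and changing the deadlines is sufficient.

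**Conclusion.** The gap in wording is real, and its consequence is small. The SAP permits the BMD-medication review and the special-interest list to be settled with treatment known. It does not say that they will be. The primary and secondary BMD analyses and the fracture summary are untouched. The exposure is limited to the medication displays that help interpret the estimand and to the special-interest outputs.

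The size cannot be quantified, because it depends on how many drugs or terms would be reclassified after step 4.

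The conclusion rests on two assumptions. One is that the steps in 3.1 are followed in the listed order, as the text states. The other is that the BMD model is fitted as specified: section 5.4.1 allows further covariates to be considered, and the classification would matter to the estimates only if BMD medication became one of them.

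This is a free or cheap improvement, and the sponsor already applies the same standard to protocol deviations.

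**What to change.** 1. In SAP 6.3, make unblinding rather than database freeze the deadline for the concomitant-medication review.
2. In SAP 7.4 and 9.6.3, require the special-interest events and terms, including the individually selected preferred terms, to be finalised and documented before step 4.
3. Label any later change, such as a MedDRA or reference-data update, as post-unblinding. Show results under the list fixed before unblinding alongside the updated ones.

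Section 3.1 needs no reordering. The cost is a few wording changes, bringing forward two decisions already planned, and possibly a second version of the special-interest tables if the list changes later.

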### 4. ANALYSIS POPULATIONS

Population	Definition / Criteria	Analyses Evaluated
All subjects enrolled (ASE)	
 
All subjects for whom a record exists on the study database, including screen failures and any subjects who were not screened but signed the informed consent form.
 
	Study Population
Pre-screen, Screen and Run- in Failures (SRIF)	
 
All subjects who were enrolled but were either pre- screen failures, screen failures, run-in failures or subjects randomised in error.
 
	Study Population
Randomised	
 
All subjects who were given a randomisation number, including subjects who were randomised in error.
 
	Study Population
(Modified) Intent to treat (ITT)	
 
All randomised subjects who received at least one dose of study treatment.
 
This population will be based on the treatment the subject was randomised to.
 
	Study Population
Safety (SAF)	
 
All randomised subjects who received at least one dose of study treatment.
 
This population will be based on the treatment the subject took for the majority of the treatment period (>50%).
 
	

Study Population

Safety

Safety excluding closed sites	
 
This population would be the same as the safety population but excluding any sites that were closed due to audit findings, failures to adhere to GCP or any other findings.
 
This population will not be used unless there is a need to exclude sites.
 
	

Study Population

Safety

Refer to Appendix 12: List of Data Displays which details the population used for each display.

#### 4.1. Protocol Deviations

Important protocol deviations (including deviations related to study inclusion/exclusion criteria, conduct of the trial, patient management or patient assessment) will be summarised and listed.

Protocol deviations will be tracked by the study team throughout the conduct of the study in accordance with the Protocol Deviation Management Plan Version 2 (26-Sep-2016) or higher.

- Data will be reviewed prior to unblinding and freezing the database to ensure all important deviations are captured and categorised on the protocol deviations dataset.
- This dataset will be the basis for the summaries and listings of protocol deviations.

A separate summary and listing of all inclusion/exclusion criteria deviations will also be provided. This summary will be based on data as recorded on the inclusion/exclusion page of the eCRF.

# 5. CONSIDERATIONS FOR DATA ANALYSES AND DATA HANDLING CONVENTIONS

## 5.1. Study Treatment & Sub-group Display Descriptors

Treatment comparisons will be displayed as follows using the descriptors as specified:

#### 1. FF/VI vs VI

	Treatment Group Descriptions								
	RandAll NG Data Displays for Reporting								
Code	Description	Description	Order [1]						
3	FF/VI 100/25mcg QD	FF/VI 100/25	2						
4	VI 25mcg QD	VI 25	1						

#### NOTES:

Order represents treatments being presented in TFL, as appropriate.
 QD = Once Daily

#### 5.2. Baseline Definitions

For all endpoints, the baseline value will be the latest pre-dose assessment with a non-missing value, including those from unscheduled visits. If time is not collected, Day 1 assessments are assumed to be taken prior to first dose and used as baseline.

Parameter	Study Assess	Study Assessments Considered As Baseline							
	Screening	Screening Day -1 Day 1 (Pre-Dose)							
Primary/Secondary E	ndpoint								
BMD	Х			Screening					
Other Endpoints									
FEV 1			X	Day 1 (Pre-Dose)					
Vital Signs			X	Day 1 (Pre-Dose)					

#### NOTES:

- Unless otherwise stated, the mean of replicate assessments at any given time point will be used as the value for that time point.
- [1] = If any additional assessments closer to Day 1 (Dose) are taken then these will be used instead.

Unless otherwise stated, if baseline data is missing no derivation will be performed and baseline will be set to missing.

#### 5.3. Multicentre Studies

In this multicentre global study, enrolment will be presented by investigative site and country.

Central randomisation was used for this study. It is likely that many centres will enrol a very small number of subjects and hence data from all participating centres will be pooled prior to analysis.

## 5.4. Examination of Covariates, Other Strata and Subgroups

#### 5.4.1. Covariates and Other Strata

The list of covariates and other strata may be used in descriptive summaries and statistical analyses, some of which may also be used for subgroup analyses. Additional covariates and other strata of clinical interest may also be considered.

Category	Details
Covariates:	Age, Gender, Baseline BMD, Visit, Baseline BMI
All models	
Covariates:	Treatment*covariate interactions will be included in the model, and if these are
To be investigated	significant (10% level) then a split model will be investigated.

## 5.4.2. Examination of Subgroups

The analysis of bone mineral density will be presented overall and by gender (males and females). For the gender analysis, each individual gender will have its own separate model fitted excluding any data from the opposite gender (split model).

There are no other planned subgroup analyses unless the treatment\*covariate interaction is shown to be significant at the 10% level, in which case subgroups will be calculated and presented in the same way as gender. For example, if smoking status was shown to be significant it would be categorised as demonstrated below and then presented by these categories.

Table 3 shows all potential subgroups that will be investigated.

Table 3	Potential	Subgroups
Iddie	i Otelitiai	Oubgioups

Covariate	Categorical or Continuous
Age	Continuous
Baseline BMI	BMI will be modelled as continuous but if it needs to be categorised for the purposes of producing summaries by subgroups the following categories will be used; < 25, 25 <= to < 30 and >= 30. This is based on the WHO definition for categorising BMI but combining the < 18.5 and 18.5 <= to <25 categories due to low number of subjects in the HZC102972 study having a BMI < 18.5.
Smoking Status	Categorical: Current or Former.

# 5.5. Multiple Comparisons and Multiplicity

No multiple comparison adjustments will be made.

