8.2. Study Design Considerations

8.2.1. Sample Size Assumptions

This study will evaluate non-inferiority in both males and females separately as key secondary measures. 56 subjects per gender per treatment would provide 80% power to demonstrate non-inferiority by comparing the lower boundary of a two-sided 95% confidence interval on the treatment difference to -1%/year assuming a true treatment difference of -0.3%/year. In study SCO40041, approximately 20% of subjects did not provide post-baseline data, therefore 70 subjects per gender per treatment will be randomized (280 total subjects). Randomization will be stratified by gender.

For the primary evaluation of BMD for the total hip, males and females will be combined, and will have >90% power to demonstrate non-inferiority by comparing the lower boundary of a two-sided 95% confidence interval on the treatment difference to -1%/year assuming a true treatment difference of -0.3%/year.

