## 7.2. Secondary Safety Analyses

## 7.2.1. Endpoint / Variables

- Bone mineral density measured at the Total Hip by Gender
- Bone mineral density measured at the Lumbar Spine L1-L4
- Bone mineral density measured at the Lumbar Spine L1-L4 by Gender

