#### **Model Specification**

- See Section 7.1.5.1.
- For the models of bone mineral density measurements by Gender, each gender will have their own model fitted excluding any data from the opposite gender (split model).

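### Three secondary non-inferiority tests are each run at one-sided 2.5% with no gate on the primary and no supportive label, so the chance of a false secondary claim can reach about 6 to 7%

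*SAP*

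**What the plan says.** The primary test is single and clear: total hip, both genders combined, FF/VI against VI. SAP 2.4 states the rule: "The 95% confidence interval will be compared to a lower bound of -1%/year in order to assess clinical non-inferiority".

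The secondary comparisons are also written as tests:

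- **By gender.** Protocol 8.2.1 says "This study will evaluate non-inferiority in both males and females separately as key secondary measures". It gives each gender 80% power by "comparing the lower boundary of a two-sided 95% confidence interval on the treatment difference to -1%/year". These comparisons set the sample size. The site is not named in that sentence, but the sensitivity tables beside it (Protocol 8.2.2, SAP 2.5) concern the total hip, so I read them as hip tests.
- **Lumbar spine overall.** Having set out the hypotheses for the hip, SAP 2.4 adds "This is also the null and alternative hypothesis for the secondary measure of BMD assessed at the L1-L4 lumbar spine". Protocol 8.1 does the same.
- **Lumbar spine by gender.** SAP 7.2.1 lists "Bone mineral density measured at the Lumbar Spine L1-L4 by Gender" as a further secondary variable under the same model, but no hypothesis or margin comparison is written for it.

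SAP 5.5 is one sentence: "No multiple comparison adjustments will be made". Neither document orders the secondaries, makes them depend on the primary, or calls them supportive or exploratory.

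**The concern.** In a bone-safety trial built on non-inferiority, a false positive is a false reassurance: a statement that the inhaled steroid does not cause unacceptable bone loss in men, in women or at the spine when it does. The usual reason for leaving safety comparisons unadjusted is to avoid missing harm. That reason runs the other way here, because an unadjusted non-inferiority test makes it easier to conclude that harm is absent.

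As written, nothing stops the report from declaring non-inferiority for one gender or for the spine after the overall hip test has failed. A reader would take each such claim to carry a 2.5% error rate. Taken together, the claims do not.

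**Working it through.** **1. Confirm the level of each test from the plan's own sample size.** Inputs: margin 1%/year, true difference 0.3%/year in the unfavourable direction and two-sided 95% interval (Protocol 8.2.1); SD 1.3%/year (SAP 2.5).

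- n per arm = 2 × SD² × (1.960 + 0.842)² / (1 - 0.3)² = 2 × 1.69 × 7.85 / 0.49 = 54.1, so 55. The protocol says 56.
- Standardised shift with 56 per arm: 0.7 / (1.3 × √(2/56)) = 2.85. Power = Φ(2.85 - 1.96) = 81.3% (80.6% using the t distribution).
- 56 / 0.8 = 70 per cell, and 4 × 70 = 280 randomised, as stated.
- With 112 per arm for the overall hip, power is 98.1%. SAP Table 2 says 98%.

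So each by-gender test was planned at the full one-sided 2.5%.

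**2. Error for the three stated tests.** Set every true difference at -1%/year. Males and females are independent because SAP 7.2.5.1 fits separate models to separate data. With equal strata, the overall statistic is (male + female)/√2. The hip-spine correlation within gender is not in the documents, so it is varied from 0 to 0.9. The critical value is 1.96, with 2,000,000 draws. Check at zero correlation: 1 - 0.975³ = 7.3%.

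| Hip-spine correlation (assumed) | At least one false claim: hip males, hip females, spine overall | Same, adding spine males and spine females |
|---|---|---|
| 0 | 7.3% | 10.5% |
| 0.2 | 7.2% | 10.2% |
| 0.5 | 6.9% | 9.6% |
| 0.8 | 6.4% | 8.3% |
| 0.9 | 6.1% | 7.6% |

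For the three tests this is 2.4 to 2.9 times the nominal 2.5%.

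**3. How much arises after a failed primary.** For the three tests, the chance of a false secondary claim while the overall hip fails is 5.5% at correlation 0.2, 5.1% at 0.5 and 4.4% at 0.8, or about 4 to 6 points over the whole range. At 0.5 that is 5.1/6.9, roughly three quarters of the total.

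**4. What a gate on the primary does.** If the overall hip is at the margin, a gated false claim requires the primary to pass falsely first, so the rate cannot exceed 2.5%. If the overall hip is truly non-inferior, the gate nearly always opens and protects less. With one gender and the spine both at the margin, two false claims remain possible. At zero correlation and with the gate always open this is 1 - 0.975² = 4.9%; overall it is about 4 to 5%.

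**5. Power under the gate** (SD 1.3%/year, true difference -0.3%/year at both sites). Per-gender hip power goes from 81.3% to 81.0% with the gate alone and to 79.6% with Hochberg added. Spine power goes from 98% to 96-97%. Power to show both genders stays at about 66%.

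**The case against.** The strongest reply is that the trial has one decision, the overall hip, that this test is untouched, and that secondary safety results in such a report are read descriptively. The display list gives this some support. In SAP Appendix 12 the -1% boundary is added only to Figure 2.3 (overall hip) and Figure 2.8 (overall spine), and the by-gender figures carry none. It can also be said that placing every true difference at the margin is the least favourable case, when the planning value is -0.3%/year.

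Part of this stands. The primary is not inflated, and the 6 to 7% is a worst-case rate, which is what an error rate at the margin means. The descriptive reading does not stand for the three stated tests. The protocol says non-inferiority will be evaluated in each gender and sizes the trial on it. SAP 2.4 writes a hypothesis for the spine. SAP Table 1, which lists departures from the protocol analysis, withdraws neither. If a descriptive reading was intended, no sentence says so.

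Two stronger readings are tempting and not supported:

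- A reader might count five secondary tests and infer a false-claim rate about four times nominal. Spine by gender has no written non-inferiority hypothesis and no margin line, so the figure of about 10% is an upper case that applies only if those two comparisons are also tested.
- A reader might add the 10% interaction screen to the false-claim rate. SAP 5.4.2 says only that a significant interaction is a case "in which case subgroups will be calculated and presented in the same way as gender". That leads to more displays, not to a non-inferiority conclusion.

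**Conclusion.** The concern holds for three secondary tests. SAP 5.5 leaves hip males, hip females and overall spine each at one-sided 2.5%, ungated and unlabelled. With all true differences at -1%/year, equal gender strata and an assumed hip-spine correlation of 0 to 0.9, the chance of at least one false secondary claim is about 6 to 7% against 2.5%, and most of it falls where the primary has failed. The overall hip test keeps its 2.5%, so the main conclusion of the trial is not at risk. What is at risk is any separate claim about one sex or the spine. This should be settled in the SAP before unblinding.

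**What to change.** Amend SAP 5.5 in one of two ways.

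**Option A, gate and labels.**
1. Test the overall total hip exactly as planned.
2. Conclude any secondary non-inferiority only if that test passes.
3. Test hip males and hip females by Hochberg: both are non-inferior if both 95% intervals clear -1%/year; otherwise one is non-inferior only if its 97.5% interval clears. Place these ahead of the overall spine, or leave them not conditional on it.
4. Report spine by gender, and any subgroup opened by an interaction test, as exploratory estimates and intervals with no non-inferiority conclusion.

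This removes every false secondary claim made after a failed primary, for the small loss of power in step 5 of the working. It leaves the residual 4 to 5% case in step 4. Full familywise control needs a complete sequence, for example testing the spine only if both genders pass. Power for the spine claim would then be at most the roughly 66% chance that both genders pass.

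The order matters. Hip by gender is what the protocol was sized on, and neither document gives a spine SD. With the spine placed first and a correlation of 0.5, per-gender hip power would be 79% at a spine SD of 1.3%/year, but 74% at 1.6 and 63% at 2.0 (assumed values). A Bonferroni split over the three tests (0.025/3 = 0.0083 each) would cut per-gender power to 68%.

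**Option B, label only.** State that all secondary bone density comparisons are supportive and that no formal non-inferiority claim will be made from them. This closes the point completely and costs only the claims.

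Both options change wording only: no new data, no added subjects, and no change to the primary test.
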